8.2.2 Method of Detecting AEs and SAEs

Adverse events can be spontaneously reported or elicited during open-ended questioning, examination, or evaluation of a participant. (In order to prevent reporting bias, participants should not be questioned regarding the specific occurrence of one or more AEs.)

8.2.3 Follow-up of AEs and SAEs

- Nonserious AEs should be followed to resolution or stabilization, or reported as SAEs if they become serious (see [APPENDIX 3](#)).
- Follow-up is also required for nonserious AEs that cause interruption or discontinuation of study treatment and for those present at the end of study treatment as appropriate.
- All identified nonserious AEs must be recorded and described on the AE page of the CRF. Completion of supplemental CRFs may be requested for AEs and/or laboratory abnormalities that are reported/identified during the course of the study.

All SAEs will be followed until resolution, until the condition stabilizes, until the event is otherwise explained, or until the participant is lost to follow-up (as defined in Section [7.3](#)).

Further information on follow-up procedures is given in [APPENDIX 3](#).

8.2.4 Regulatory Reporting Requirements for SAEs

- Prompt notification by the investigator to the Sponsor of SAEs is essential so that legal obligations and ethical responsibilities towards the safety of participants and the safety of a product under clinical investigation are met.
- An investigator who receives an investigator safety report describing SAEs or other specific safety information (eg, summary or listing of SAEs) from the Sponsor will file it along with the IB and will notify the IRB/IEC, if appropriate according to local requirements.

Sponsor or designee will be reporting AEs to regulatory authorities and ethics committees according to local applicable laws including European Directive 2001/20/EC and FDA Code of Federal Regulations 21 CFR Parts 312 and 320. A SUSAR (Suspected, Unexpected Serious Adverse Reaction) is a subset of SAEs and will be reported to the appropriate regulatory authorities and investigators following local and global guidelines and requirements.

8.2.5 Pregnancy

If, following initiation of the study treatment, it is subsequently discovered that a participant is pregnant or may have been pregnant at the time of study exposure, including during at least 5 half-lives after product administration, the investigator must immediately notify PRA Drug Safety of this event and complete and forward a Pregnancy Surveillance Form to PRA Drug Safety within 24 hours of awareness of the event and in accordance with reporting procedures described in [APPENDIX 3](#).

In most cases, the study treatment will be permanently discontinued in an appropriate manner (eg, dose tapering if necessary for participant safety).

Any pregnancy that occurs in a female partner of a male study participant should be reported to PRA Drug Safety. In order for the Sponsor or designee to collect any pregnancy surveillance information from the female partner, the female partner must sign an informed consent form for disclosure of this information. Information on this pregnancy will be collected on the Pregnancy Surveillance Form.

8.2.6 *Laboratory Test Result Abnormalities*

The following laboratory test result abnormalities should be captured on the AE CRF page. If a laboratory test result meets the definition of a serious adverse event, the laboratory test result should be reported as an SAE and submitted to PRA Drug Safety as specified in [APPENDIX 3](#).

- Any laboratory test result that is clinically significant or meets the definition of an AE or SAE
- Any laboratory test result abnormality that required the participant to have study treatment discontinued or interrupted
- Any laboratory test result abnormality that required the participant to receive specific corrective therapy

It is expected that wherever possible, the clinical rather than laboratory term would be used by the reporting investigator (eg, anemia versus low hemoglobin value).

8.2.7 *Potential Drug Induced Liver Injury (DILI)*

Wherever possible, timely confirmation of initial liver-related laboratory abnormalities should occur prior to the reporting of a potential DILI event. All occurrences of potential DILIs, meeting the defined criteria, must be reported as SAEs (see Section [8.2](#) and [APPENDIX 3](#) for reporting details).

Potential DILI is defined as:

- 1) ALT or AST elevation > 3 times upper limit of normal (ULN)
AND
- 2) Total bilirubin > 2 times ULN, without initial findings of cholestasis (elevated serum alkaline phosphatase),
AND
- 3) No other immediately apparent possible causes of aminotransferase elevation and hyperbilirubinemia, including, but not limited to, viral hepatitis, pre-existing chronic or acute liver disease, or the administration of other drug(s) known to be hepatotoxic.

8.2.8 *Other Safety Considerations*

Any significant worsening noted during interim or final physical examinations, electrocardiogram, any other potential safety assessment required or not required by protocol should also be recorded as a nonserious or serious AE, as appropriate, and reported accordingly.

8.3 *Overdose*

All occurrences of overdose must be reported as SAEs (see Section [8.2](#)).

An overdose is defined as the accidental or intentional administration of any dose of a product that is considered both excessive and medically important. All occurrences of overdose must be reported as an SAE (see Section 8.2).

BMS-986231

Since there is limited clinical experience with BMS-986231, there is no current knowledge with overdosing, hence no specific guidance is currently available. In case of acute overdose, it is not known if dialysis would accelerate drug clearance. BMS-986231 produces vasodilation as a component of its hemodynamic effects. Thus, the most immediate adverse effect in the case of overdose of BMS-986231 may be hypotension, mediated at least in part by mechanisms similar to the hypotensive activity of IV nitroglycerin through activation of soluble guanylate. No specific pharmacologic antidote to HNO effects exists. In previous studies with BMS-986231 in healthy volunteers and advanced HF subjects, cessation of drug was adequate to restore blood pressure within 1-2 hours. In the event of an overdose, the infusion should be discontinued, and other therapies administered concurrently that have vasodilatory effects should be discontinued. Volume repletion, either orally or intravenously, can be used to counter the clinical effects of HNO mediated vasodilation, but should be used with extreme caution in decompensated HF subjects. If marked hypotension occurs, appropriate treatment, including IV pressor agents may be required to support blood pressure.

Furosemide

The principal signs and symptoms of overdose with furosemide are dehydration, blood volume reduction, hypotension, electrolyte imbalance, hypokalemia and hypochloremic alkalosis, and are extensions of its diuretic action. The acute toxicity of furosemide has been determined in mice, rats and dogs. In all 3, the oral LD50 exceeded 1000 mg/kg body weight, while the IV LD50 ranged from 300 to 680 mg/kg. The acute intragastric toxicity in neonatal rats is 7 to 10 times that of adult rats. The concentration of furosemide in biological fluids associated with toxicity or death is not known. Treatment of overdosage is supportive and consists of replacement of excessive fluid and electrolyte losses. Serum electrolytes, carbon dioxide level and blood pressure should be determined frequently. Adequate drainage must be assured in patients with urinary bladder outlet obstruction (such as prostatic hypertrophy). Hemodialysis does not accelerate furosemide elimination.

8.4 Safety

Planned time points for all safety assessments are listed in the Schedule of Activities (Section 1.3).

8.4.1 Physical Examinations

Refer to Schedule of Activities (Section 1.3).

8.4.2 Vital Signs

Refer to Schedule of Activities (Section 1.3). Vital Signs (blood pressure and heart rate) will be recorded after the participant has rested quietly for at least 5 minutes in a supine position.

8.4.3 *Peripheral Oxygen Saturation*

Refer to Schedule of Activities (Section 1.3). Peripheral oxygen saturation will be recorded after the participant has rested quietly for at least 5 minutes in a supine position.

8.4.4 *Electrocardiograms*

Refer to Schedule of Activities (Section 1.3).

All ECG recordings must be performed using a standard high-quality, high-fidelity machine equipped with computer-based interval measurements and automated interpretation. Automated ECG intervals and HR will be captured or calculated, and changes of the T-wave and U wave morphology will be documented. ECG will be recorded after the participant has rested quietly for at least 5 minutes in a supine position.

8.4.5 *Continuous Cardiac Monitoring (Telemetry)*

Refer to Schedule of Activities (Section 1.3).

Continuous ECG monitoring will be performed to help monitor patient safety, primarily to detect ventricular and atrial arrhythmias. The site will follow their normal operating procedures established for ECG monitoring by trained staff. Clinically significant findings from the monitoring will be recorded as AEs and SAEs per investigator's decision, and at the investigator's discretion the infusion may be discontinued for clinically significant arrhythmias.

8.4.6 *Clinical Safety Laboratory Assessments*

Investigators must document their review of each laboratory safety report. Subjects will have laboratory tests performed as described in the following sections. A central/local laboratory will perform the analyses and will provide reference ranges for these tests.

Laboratory assessments for screening

The following laboratory tests will be performed as part of the screening evaluation. Results will be recorded in the study eCRF.

Hematology

- Hemoglobin
- Hematocrit
- White blood cell count and differential
- Platelet count

Serum Chemistry

- Aspartate Aminotransferase (AST, SGOT)
- Alanine Aminotransferase (ALT, SGPT)
- Blood Urea Nitrogen (BUN)
- Electrolytes
 - Sodium
 - Potassium
- Serum Creatinine (Scr)

- eGFR by equation used locally

Other Analyses

- BNP or NT-pro BNP (according to local lab availability) will be performed at screening.
- Pregnancy test (WOCBP only: screening, pre-dose (before start of infusion) in each treatment period).

On each treatment day, the study drug infusion could start without waiting for the results of the laboratory assessments done in the morning of the treatment day at the study facility if the following criteria are met:

- The results of the laboratory assessment at screening / previous period are within ranges compatible with inclusion criteria.
- The study participant was medically stable with no signs of overt HF decompensation or deteriorating signs and symptoms of congestion and without change in medication since the screening visit / previous period.

Laboratory Assessments During Study

The following laboratory tests will be performed and submitted to the Laboratory or Sponsor designated vendors for analysis as per the Study Assessment and Procedures.

Analyses		Timing
Hematology	
 • Hemoglobin • Hematocrit • White blood cell count, including differential • Platelet count 	H0 (before start of infusion), H4 and H8 on each treatment day
Serum Chemistry	
 • Aspartate Aminotransferase (AST, SGOT) • Alanine Aminotransferase (ALT, SGPT) • Total bilirubin • Serum Creatinine (Scr) • eGFR • BUN 	H0 (before start of infusion), H4 and H8 on each treatment day
	
 • Electrolytes: Na, K, Creatinine, eGFR • Bicarbonate, free water clearance 	H0 (before start of infusion), H4, H5, H6, H7, H8 on each treatment day
Furosemide	
 • Furosemide plasma concentration 	Please refer to Table 7
Urinalysis	
 • Fractional excretion of sodium • Fractional excretion of potassium • Urine Na, K, bicarbonate, creatinine, urea, phosphate, chloride, urine albumin-to-creatinine ratio (uACR) • Furosemide urinary concentration • Exploratory urinary biomarkers: including but not limited to urine kidney injury molecule-1 (KIM1) 	Please refer to Table 8

The detailed methods for specimen collection, handling, processing, shipping, and storage will be supplied in the Investigator's Laboratory Manual provided by the Laboratory.

8.4.7 *Suicidal Risk Monitoring*

Not applicable.

8.4.8 *Imaging Safety Assessment*

Any incidental findings of potential clinical relevance that are not directly associated with the objectives of the protocol should be evaluated and handled by the investigator as per standard medical/clinical judgment.

8.5 Pharmacokinetics

Pharmacokinetic data of furosemide and BMS-986231 (and its metabolites) will be derived from plasma and urine concentration versus time data.

The primary possible PK parameters to be assessed for BMS-986231 (and its metabolites) and furosemide are included in [Table 6](#):

Table 6: Potential Pharmacokinetic Parameters Calculated for Furosemide

Cmax	Maximum observed plasma concentration
AUC(INF)	Area under the concentration-time curve from time 0 extrapolated to infinity
AUC(0-T)	AUC from time 0 up to time T, where T is the last time point with concentrations above the lower limit of quantitation
Ae	Total amount recovered in urine
% UR	Percent urine recovery
CLR	Renal clearance of drug from plasma

Additional PK parameters may be calculated as deemed appropriate.

The plasma and urine samples for furosemide and BMS-986231 (and its metabolites BMT-284730 and BMT-279554) will be analyzed by a quantitative liquid chromatography with tandem mass spectrometry (LC-MS/MS) assay.

Blood samples will be collected for PK assessments as described in [Table 7](#). Urine samples can be taken from the urine collection intervals as described in [Table 8](#). Detailed instructions for the PK blood and urine collection, labeling, processing, storage, and shipping will be provided to the site in the Laboratory Manual.

In addition, collect a PK sample from the patient when the dose is lowered due to a safety event and also at time of early discontinuation of study drug. The sample should be collected immediately before or after the decision to change the dose was made.

Detailed instructions for the PK blood collection, labeling, processing, storage, laboratories performing the analyses, and shipping will be provided to the site in the procedure manual.

8.5.1 Blood Sampling and Urine Collection Intervals for PK and Efficacy

Blood sampling time points for furosemide, BMS-986231 (and its metabolites), Na and K are indicated in [Table 7](#).

Table 7: Blood Sampling for Furosemide, BMS-986231 (and its metabolites)

Study Day of Sample Collection (of Each Period)	Event	Time (Relative To Start of Infusion of BMS-986231) Hour: Min	Blood Sample
1	Before start of infusion ^a	00:00	X
1	2.0 hours ^a	02:00	X
1	4.0 hours ^b	04:00	X
1	5.0 hours	05:00	X
1	6.0 hours	06:00	X
1	8.0 hours (EOI) ^c	08:00	X
1	10.0	10:00	X
1	Dose lowered due to safety event	Misc.	X

^a This time-point is not applicable for furosemide analysis

^b Just before furosemide bolus

^c EOI=End of Infusion, This sample should be taken immediately prior to stopping the infusion (preferably within 2 minutes prior to the end of infusion). If the end of infusion is delayed to beyond the nominal infusion duration, the collection of this sample should also be delayed accordingly. If end of infusion occurs prior to 8 hours after start of infusion (H8), the end of infusion should be considered early discontinuation. In case of an early discontinuation, the timing for the assessments will be adapted accordingly, ie, H8 will be immediately after end of infusion and H10 will be 2 hours after infusion.

Time points for urine collection intervals are presented in [Table 8](#).

Table 8: Urine Collection Intervals for Urine Output and Assessment of Furosemide, BMS-986231, K, Na, P, Bicarbonate, Creatinine, and Cl

Study Day of Sample Collection (of Each Period)	Event	Time (Relative To Start of Infusion of BMS-986231) Hour: Min	Urine Sample Collection Intervals ^a
1	Before start of infusion	00:00	X
1	2.0 hours	02:00	0-2 hours
1	4.0 hours ^b	04:00	2-4 hours
1	5.0 hours	05:00	4-5 hours
1	6.0 hours	06:00	5-6 hours
1	7.0 hours	07:00	6-7 hours
1	8.0 hours (EOI) ^c	08:00	7-8 hours
1	10.0 hours	10:00	8-10 hours

^a In the first 4 hours of the study drug infusion, and before furosemide bolus, urine collection will be done every 2 hours, thereafter the void will be hourly

^b Just before furosemide bolus

^c EOI=End of Infusion, This sample should be taken immediately prior to stopping the infusion (preferably within 2 minutes prior to the end of infusion). If the end of infusion is delayed to beyond the nominal infusion duration, the collection of this sample should also be delayed accordingly. If end of infusion occurs prior to 8 hours after start of infusion (H8), the end of infusion should be considered early discontinuation. In case of an early discontinuation, the timing for the assessments will be adapted accordingly, ie, H8 will be immediately after end of infusion and H10 will be 2 hours after infusion.

[REDACTED]

[REDACTED]

[REDACTED]

[REDACTED]

[figure not shown]
[REDACTED]

[REDACTED]

[REDACTED]

[REDACTED]

[REDACTED]

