[REDACTED]				Washout between periods should be at least 7 days and no more than 4 weeks.
[REDACTED]	■		■	[REDACTED]
[REDACTED]	■		■	[REDACTED]

^a If end of infusion occurs prior to 8 hours after start of infusion (H8), the end of infusion should be considered early discontinuation. In case of an early discontinuation, the timing for the assessments will be adapted accordingly, ie, H8 will be immediately after end of infusion, H9 will be 1 hour after end of infusion, H10 will be 2 hours after end of infusion, H11 will be 3 hours after end of infusion, and H11.5 will be 3.5 hours after end of infusion, as applicable.

STUDY ACKNOWLEDGMENT/DISCLOSURE

I understand that this protocol contains information that is confidential and proprietary to Bristol-Myers Squibb Company (BMS). Any supplemental information that may be added to this document is also confidential and proprietary to BMS and must be kept in confidence in the same manner as the contents of this protocol.

I have read the original protocol and agree that it contains all necessary details for carrying out the study as described. I will conduct this protocol as outlined therein and will make a reasonable effort to complete the study within the time designated.

I will provide copies of the protocol and access to all information furnished by BMS to study personnel under my supervision. I will discuss this material with them to ensure that they are fully informed about the investigational product and the study.

I will provide protocol information to my Institutional Review Board(s) [IRB(s)] or Independent Ethics Committee(s) [IEC(s)]. I understand that original protocol/revised protocols must be reviewed by the Institutional Review Board or Independent Ethics Committee overseeing the conduct of the study and approved or given favorable opinion by all necessary Health Authorities before implementation unless to eliminate an immediate hazard to subjects.

I agree that the contents of the protocol may not be disclosed to any other person or entity or used for any other purpose without the prior written consent of BMS. The foregoing shall not apply to disclosure required by governmental regulations or laws; however, I will give prompt notice to BMS of any such disclosure.

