After a dose reduction, the dose cannot be increased again. Study drug will be permanently discontinued after it has been down titrated once, and criteria for dose reduction or interruption has been met again.

If an infusion in a given period is discontinued, patients remain eligible to complete the subsequent period.

Any decision to lower the dosage level of study drug or discontinue study drug should be based on the investigator's assessment of the patient's overall clinical stability, in the context of appropriate ongoing monitoring of the patient's condition.

A 50% dosage adjustment downward will be achieved by decreasing the rate of study drug infusion from 20 mL/H to 10 mL/H.

Furosemide will be administered through an IV bolus injection at H4 of study drug infusion. In the event the study drug has been reduced, furosemide injection is administered at H4 as planned. If the study drug has been temporarily interrupted, then restarted, furosemide will be administered after at least 4 hours of effective study drug infusion.

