9.4.1.2 Secondary Efficacy Analysis

Secondary efficacy analyses will be performed using the randomized population. The FeNa, FeK, furosemide urinary and plasma concentration and the ratio of urinary sodium to urinary furosemide will be calculated at each time point over 4-hour urine/plasma collection after a bolus injection of 40 mg furosemide while receiving BMS-986231 or placebo. All data will be listed and tabulated. Graphical presentations may be provided.

A similar analysis as described in the primary efficacy analysis section will be conducted on the values derived at the 8-hour time point (8 hours after start of infusion).

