15.3 Effect of BMS-986231 on furosemide concentration

Furosemide urinary and plasma concentrations and the ratio of urinary sodium to urinary furosemide will be calculated at each time point over 4-hour urine/plasma collection after a bolus injection of 40 mg furosemide while receiving BMS-986231 or placebo

Descriptive statistics (n, mean, SD, %CV, median, min, and max) will be used to summarize the absolute difference and the percent change from placebo of furosemide urine concentration, furosemide plasma concentration and the ratio of urinary sodium to urinary furosemide at 8 h by treatment.

Paired profiles of furosemide urine concentration, furosemide plasma concentration and the ratio of urinary sodium to urinary furosemide (4 h after furosemide dosing) will be provided for a visual representation of the data.

[REDACTED]

[REDACTED]

[REDACTED]

[REDACTED]

[REDACTED]

[REDACTED]

[REDACTED]

[REDACTED]

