Appendix 4: List of Tables, Figures, and Listings

List of Tables and Figures:		
Output	Title	Analysis Set
Section 14.1 – Disposition and Demographic Data		
Table 14.1.1	Summary of Analysis Sets	All Subjects
Table 14.1.2	Summary of Subject Disposition	All Subjects
Table 14.1.3.1	Summary of Demographics	Randomized
Table 14.1.3.2	Summary of Demographics	Per Protocol
Table 14.1.4	Summary of Dosing	Safety
Section 14.2 – Efficacy Data		
Table 14.2.1.1	Summary of Urinary Output	Per Protocol
Figure 14.2.1.2	Plot of Mean (+SD) Urinary Output over Time	Per Protocol
Figure 14.2.1.3.1	Barchart of Mean Urinary Output over Time	Per Protocol
Figure 14.2.1.3.2	Barchart of Individual Urinary Output over Time	Per Protocol
Table 14.2.1.4	Statistical Analysis of the Volumes of Urinary Excretion	Per Protocol
Figure 14.2.1.5	Plot of Paired Urinary Output by Treatment	Per Protocol
Figure 14.2.1.6	Q-Q-Plot of Difference BMS-986231 – Placebo	Per Protocol
Table 14.2.2.1	Summary of Fractional Excretion of FeNa and FeK	Per Protocol
Figure 14.2.2.2.1	Barchart of Mean Fractional Excretion over Time	Per Protocol
Figure 14.2.2.2.2	Barchart of Individual Fractional Excretion over Time	Per Protocol
Table 14.2.2.3	Statistical Analysis of the Fractional Excretion	Per Protocol
Figure 14.2.2.4	Plot of Paired Fractional Excretion	Per Protocol
Table 14.2.3.1	Summary of Natriuresis	Randomized
Figure 14.2.3.2	Plot of Paired Natriuresis	Randomized
Table 14.2.4.1	Summary of Furosemide Concentration and Ratio of Urinary Sodium to Urinary Furosemide	Randomized
Figure 14.2.4.2	Plot of Paired Furosemide Concentration and Ratio of Urinary Sodium to Urinary Furosemide	Randomized
Table 14.2.5	Summary of eGFR and Creatinine Levels	Randomized
Table 14.2.6	Summary of Renal and Urinary Biomarkers	Randomized
Table 14.2.7	Summary of Body Weight	Randomized
Table 14.2.8	Summary of Body Bio-Impedance	Randomized
Table 14.2.9	Summary of Ultrasound Indices of Congestion	Randomized
Table 14.2.10	Summary of Lung Ultrasound Indices of Pulmonary Congestion	Randomized
Table 14.2.11	Summary of Pulmonary B-lines	Randomized
Section 14.2 – Pharmacokinetic Data		
Table 14.2.12.1	Summary of Furosemide Plasma Concentrations	Randomized
Table 14.2.12.2	Summary of Furosemide Urine Recovery by Interval	Randomized

Table 14.2.12.3	Summary of Furosemide Urine Recovery	Randomized
Table 14.2.12.4	Summary of BMS-986231 and Metabolite Plasma Concentrations	Randomized

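### After an early infusion stop the sample taken at the stop becomes the 'H8' sample, so the 8-hour furosemide endpoints can pair values from different times after the bolus, and no SAP rule prevents it

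*Protocol*

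**What the plan says.** **Bolus.** Protocol 6.4: "Furosemide will be administered through an IV bolus injection at H4 of study drug infusion". In an uninterrupted infusion, H8 is therefore 4 h after the bolus.

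**Endpoint.** Protocol 9.3.2 and SAP 5.2.1 set the secondary endpoints (FeNa, FeK, urinary and plasma furosemide, urinary sodium/furosemide ratio) at 8 hours from the start of infusion. Protocol 9.4.1.2 plans an analysis like the primary one, a paired t-test, "conducted on the values derived at the 8-hour time point (8 hours after start of infusion"). SAP 15.3 summarises the furosemide variables descriptively at 8 h and places its plots at the same point: "Paired profiles of furosemide urine concentration, furosemide plasma concentration and the ratio of urinary sodium to urinary furosemide (4 h after furosemide dosing").

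**Early stop.** Protocol 8.5.1, Table 7 footnote c (blood): "If end of infusion occurs prior to 8 hours after start of infusion (H8), the end of infusion should be considered early discontinuation", after which "H8 will be immediately after end of infusion and H10 will be 2 hours after infusion". Table 8 footnote c (urine) has the same rule: "In case of an early discontinuation, the timing for the assessments will be adapted accordingly, ie, H8 will be immediately after end of infusion". Schedule of Activities footnote a extends it to later times: "H8 will be immediately after end of infusion, H9 will be 1 hour after end of infusion".

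**Analysis set.** Protocol 9.4.1.2 uses the randomized population. SAP Appendix 4 assigns Table 14.2.4.1, "Summary of Furosemide Concentration and Ratio of Urinary Sodium to Urinary Furosemide", to the Randomized set. The SAP 9.0 grid puts other efficacy analyses under treated per protocol, and SAP 15.2 says the same of secondary efficacy. SAP 15.3 names no set.

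**The concern.** The label H8 carries two meanings. In a completed period it is a fixed time after the bolus. In a stopped period it is whenever the infusion ended. An analysis by nominal label then pairs a patient's value from less than 4 h after the bolus with that patient's 4 h value from the other period. Plasma furosemide falls after an IV bolus, so the earlier value is higher for reasons unrelated to study drug.

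Patients whose infusion is discontinued remain eligible for the other period (Protocol 6.4), so such pairs can form. The stopping criteria in 6.4 are based on low blood pressure, and BMS-986231 is a vasodilator, so stops are plausibly more common on active drug. With about 20 patients, a single mistimed pair can visibly move a mean percent change.

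**Working it through.** The plan gives no figure to reproduce for this point. The check is one of timing, then of size under a stated assumption.

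**Inputs from the documents.** Bolus at H4 (Protocol 6.4). 'H8' at the stop and 'H10' 2 h later (8.5.1). Post-dose PK window ±15 min (1.3). Plasma furosemide sampled at H4, H5, H6, H8 and H10 (Table 7). Urine collected until 2 h after the stop (4.1). About 20 patients (9.1).

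**Assumption.** First-order decline of plasma furosemide with a half-life t of 1, 2 or 3 h. The documents give no half-life.

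**Formulas**, for a stop at clock hour T between H4 and H8, with the placebo period completed:
- time of 'H8' after the bolus = T − 4, against 8 − 4 = 4 h on placebo
- mismatch = 8 − T
- false plasma ratio = 2^((8 − T)/t)
- shift in mean percent change from one such patient among 20, the others unchanged = (ratio − 1) × 100/20

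| Stop | 'H8', h after bolus | 'H10', h after bolus | False ratio, t = 1 / 2 / 3 h | Shift in mean, points |
|---|---|---|---|---|
| H5 | 1 | 3 | 8.0 / 2.8 / 2.0 | +35.0 / +9.1 / +5.0 |
| H6 | 2 | 4 | 4.0 / 2.0 / 1.6 | +15.0 / +5.0 / +2.9 |
| H7 | 3 | 5 | 2.0 / 1.4 / 1.3 | +5.0 / +2.1 / +1.3 |
| H7.5 | 3.5 | 5.5 | 1.4 / 1.2 / 1.1 | +2.1 / +0.9 / +0.6 |

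Example, stop at H5 and t = 2 h: 2^(3/2) = 2.83, and (2.83 − 1) × 100/20 = 9.1.

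Of these four stop times, only H6 has a sample scheduled at bolus+4 h, and it carries the label H10. A relabelled value meets the ±15 min window only if the stop comes in the last 15 minutes.

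**Does anything downstream correct it?**
- SAP Appendix 3 reproduces footnote c without the early-stop sentences, so the SAP is silent on the rule.
- Actual sampling times go into the eCRF (Protocol 1.3), but SAP 15.3 does not use them.
- SAP 8.1.5 excludes unscheduled measurements from summaries and analysis. An extra bolus+4 h sample taken on a site's own initiative would be dropped.

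**Outside the table.** For a stop before H4, the 'H8' sample precedes any bolus, and the documents do not say whether furosemide is then given. For FeNa and FeK, SAP 15.2 uses interval totals, so the problem there is a shortened interval. A stop in the placebo period would bias plasma the other way.

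**The case against.** Several points against the concern stand.

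- **Inclusion is not settled.** A reader might infer from Appendix 4 that early stoppers are certainly analysed. SAP 9.0 and 15.2 point to the per-protocol set, whose definition does not say whether a patient with an early stop qualifies.
- **The SAP comparison is descriptive.** SAP 15.3 plans no test, and SAP 3.0 says that the SAP supersedes the protocol's statistics. Medians, ranges and patient listings would help expose one extreme pair. Even so, Protocol 9.4.1.2 plans a paired test, and SAP 7.1 declares no changes from protocol.
- **The literal endpoint is 8 hours after the start.** On that wording a sample from H5 does not qualify. But the protocol names that sample H8 and the SAP does not say which reading governs. The laboratory manual and table shells are not available to settle it.
- **A sample at the stop already exists.** Protocol 8.5 requires a PK sample at early discontinuation, so an EOI label adds no blood draw.
- **Bolus+4 h is not neutral.** Protocol 9.3.2 speaks of values while on BMS-986231. After a stop at H5, a bolus+4 h value is 3 h off drug. Section 2 says that preclinical effects partially resolve within 60 minutes of stopping. Using that sample is a choice of question and should be stated as one.

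A reader might also infer that the trial would report a false rise in furosemide exposure in both plasma and urine. The documents do not support that. They give no frequency of early stops. Urine values come from collection intervals, so plasma decay sizes neither urinary furosemide nor the sodium/furosemide ratio.

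**Conclusion.** The concern holds in limited form. Followed as written, the sampling rule puts an early stopper's 8-hour plasma and urine furosemide values and sodium/furosemide ratio at less than 4 h after the bolus, and the SAP neither excludes nor re-times them. This is an explicit rule that mistimes a within-patient comparison, not merely a missing detail.

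The plasma artefact is large for stops at H5 to H6 and small near H8. The figures rest on the assumed half-life of 1 to 3 h, a stop after the bolus in the BMS-986231 period, a completed placebo period, and retention of the patient in the analysis set. Only the timing mismatch is established for the urine measures. The primary 4-hour volume is not part of this point. It should be corrected before analysis, but it affects secondary, largely descriptive results.

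**What to change.** 1. **SAP 15.3.** Define the 8-hour endpoint by actual time since the bolus: 4 h, within ±15 min. Do not accept an early-stop sample as H8 because of its label; list it as EOI. Where an early stopper has no 4 h value, treat the 8-hour value as missing. Add a supportive comparison with the placebo sample at the same time after the bolus (H5 or H6) where one exists. Cost: wording and programming, using times already recorded. Timing from the bolus also covers interrupted infusions, where Protocol 6.4 ties furosemide to at least 4 h of effective infusion.
2. **Protocol Tables 2, 7 and 8.** Label the early-stop sample EOI and keep a scheduled blood and urine sample at bolus+4 h. Flag values taken after the stop as off-drug. Cost: one sampling point in early stoppers, plus urine collection beyond the current 2 h after the stop when the stop is before H6. The required 3.5 h stay covers bolus+4 h for stops from H4.5 (4.5 + 3.5 = 8); an earlier stop would need up to about half an hour more.
3. **Analysis set.** State one set for these endpoints in SAP 9.0, 15.2, 15.3 and Appendix 4, and say how early stoppers are classified in the per-protocol set. Reconcile the descriptive SAP analysis with the paired test in Protocol 9.4.1.2.
4. **H8 timing.** Footnote c places the sample just before the infusion ends in one sentence and just after it for early stops in another. Reconcile the two, and state how stops before H4 are handled in the analysis.
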